9.5. DATA ANALYSIS PLAN

The recordings of online consent (Zoom), for Phase 3, will be stored on a study computer and saved to a secure password encrypted server. As described above, participants will be asked to complete the (SUS). The SUS yields a single number representing a composite measure of the overall usability of the system being studied. Adjustments and modifications to The Back2Play App will be made before commercializing the product.

We will collect and report descriptively all demographic information, injury-related data (type, mechanism of injury, numbers of injuries), youth premorbid health history. Descriptive statistics such as means, medians, and frequencies will be reported where appropriate. Baseline comparisons will be performed between those that use The App and those whose recovery involved Usual Care with variables of mechanism of injury, age, sex, school performance and concussion history. These variables will be-analyzed using Pearson Chi Squared Cross Tabulations, T-Test and ANCOVA, to ensure the groups are similar. We will also evaluate agreement of the algorithm with the self-reported stage of recovery participants input using these same statistics.

The dichotomous variable, repeat injuries (coded as yes or no), will be analyzed using multivariate logistic regression and resulting odds ratios to determine if using The Back2Play App decreases risk of repeat injury. Confounders of age, gender, number of symptoms, time since last injury and comorbidities of premorbid mental health issues or learning disabilities will be examined as to their potential impact on outcomes. Many of these variables will be correlated with each other and these correlations will need to be examined carefully before they are entered into the analyses.

Time to symptom resolution will be analyzed using survival curves with Multivariate Cox regression analysis. Cox regression (also called proportional hazard models) is a method of survival analysis that models the time until some event as a function of either continuous or categorical predictors, allowing for the fact that not all subjects will experience the events of interest and that they will occur at different times.

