symptoms or more at 1 month post concussive injury. There is now a prediction risk score for PCS^{18} which helps clinicians determine at presentation which children will go onto have PCS or symptoms past one month. All children/youth still must be monitored to determine if their symptoms resolve early or if they are among the 50% of children/youth at risk for symptoms lasting greater than one month, or one of the 13% that are symptomatic beyond three months post-injury. There is now a growing body of evidence to show that with education, comprehensive assessment and rehabilitation, symptom resolution may occur sooner and secondary problems like depression and school failure can be prevented. 19

Multiple concussions are common in the pediatric population

Swaine et al.²⁰ found that concussed children are twice as likely to receive a subsequent head injury within 12 months. Moreover, more than 30% of high school athletes have been shown to sustain multiple head injuries.²¹⁻²² Greater than 34% of children who received service at the ABI Follow-Up Clinic at MCH had experienced multiple concussions, with 17% experiencing three or more injuries.

Children who have sustained multiple concussions often have prolonged and severe symptoms including learning difficulties, behavioural problems, debilitating headaches, visual problems, and impaired memory. 23-25 Concussion often results in substantial long-term cognitive and behavioural disturbances that can have significant impact on the quality of life of individuals. 26-27 Our own research supports these findings as we found that children with mild injuries had decreased quality of life and neuropsychological impairment at five years post-injury compared to norms for age. 28 This evidence, in combination with the growing body of knowledge surrounding chronic traumatic encephalopathy (CTE) (where degeneration has been demonstrated in the brains of athletes who have had multiple concussions, some as early as 18 years of age 29-30), commands us to prevent these repetitive injuries even though we may not yet fully understand the mechanisms and individual propensity to this debilitating condition.

Current approaches to concussion management have limitations

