3. METHODS

Description of Population and Sample

Our population consists of male and female youth aged 10-18 years that have been diagnosed with a concussion by a physician. Youth presenting to the David Braley Clinic, McMaster Children's Hospital, HWCDSB, Montreal Children's Hospital or physicians in the community will be randomly assigned to the intervention or control groups.

A clinically significant effect of 10% decrease in repeat head injury and 10% decrease in recovery time would be of interest. The sample size calculation was done using parameters with a two sided significance of 0.05 and a power of 0.8 and based on our primary outcome of repeat head injury which is a binomial variable. Our anticipated incidence rate was compared to two rates of incidence in clinical settings and in the literature:

- 16% rate common in the literature
- our anticipated 2% rate with adherence to protocols (from previous B2P study) N=128
- 37% rate from concussion clinic at MCH and
- 13% rate of our pilot data N=100.

The larger number will be sought (sample size takes into consideration 20% refusal rate and loss to follow up) therefore we will recruit N=160. With an average of 25-30 new cases per month from the sources outlined above, 60% consent rate, and 12 months recruitment, it is feasible to attain this sample of youth.

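### Baseline significance tests cannot show that the arms are similar, and concussion history is tested and described but is not among the listed adjustment variables

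*Combined protocol and SAP*

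**What the plan says.** Section 9.5 plans comparisons between App and Usual Care participants on five baseline variables: mechanism of injury, age, sex, school performance and concussion history. It states the purpose directly: "These variables will be-analyzed using Pearson Chi Squared Cross Tabulations, T-Test and ANCOVA, to ensure the groups are similar". It gives no significance level, no size of imbalance that would matter, and no action if the groups differ. The same paragraph says that injury data, including numbers of injuries, will be reported descriptively.

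The paragraph on repeat injury then gives the adjustment candidates: "Confounders of age, gender, number of symptoms, time since last injury and comorbidities of premorbid mental health issues or learning disabilities will be examined". Concussion history is not among them. The paragraph on time to symptom resolution specifies a multivariable Cox model but names no covariates of its own.

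Section 2 reports a cohort study that "found that concussed children are twice as likely to receive a subsequent head injury within 12 months". It also says that more than 34% of children at the follow-up clinic had multiple concussions, and that children with multiple concussions often have prolonged and severe symptoms. Section 8 names repeat head injury and time to symptom resolution as the two primary outcomes.

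**The concern.** Two things look wrong, and they are linked.

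First, the tests are given a job they cannot do. Randomisation makes the null hypothesis of every baseline test true by design. A p-value above 0.05 therefore tells the reader nothing about whether the two groups actually drawn are close enough. With no margin stated, non-significance stands in for a claim of similarity.

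Second, the variable that the protocol's own background connects to both primary outcomes is checked this way but is not put forward for adjustment. If the draw happened to leave more participants with prior concussion in one arm, the effect estimates for repeat injury and symptom duration could both carry that imbalance. The analysis plan would not already contain the correction. Participants and researchers are unblinded (section 6), so a covariate added after the data are seen would be open to challenge.

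**Working it through.** **Inputs from section 3.** The sample size uses a "two sided significance of 0.05 and a power of 0.8". Scenario 1 is "16% rate common in the literature" against "our anticipated 2% rate with adherence to protocols (from previous B2P study) N=128". Scenario 2 is "37% rate from concussion clinic at MCH and" "13% rate of our pilot data N=100". The recruitment target is 160 after a 20% allowance, with equal allocation (section 6).

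**Reproducing the plan's sizes.** A two-proportion formula with pooled variance and no continuity correction gives:
- 16% vs 2%: 65 per arm, 130 in total (plan: 128).
- 37% vs 13%: 50 per arm, 100 in total (plan: 100).
- 128 / 0.8 = 160 (plan: 160).

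So the comparison has 80 per arm if everyone randomised is included, and 64 per arm if 128 remain.

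**What a baseline test says about a realised split.** The Pearson test without continuity correction is z = d / sqrt(2p(1 − p)/n), where d is the difference in proportions, p the pooled proportion and n the number per arm. The base rate of about 34% is borrowed from the clinic figure in section 2. The 0.05 level is assumed, because section 9.5 gives none.
- 17/64 vs 27/64: d = 0.156, p = 0.344, z = 1.86, p-value 0.063. Not significant.
- 21/80 vs 33/80: d = 0.150, p = 0.3375, z = 2.01, p-value 0.045. Significant.

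The larger gap passes and the smaller one is flagged. The label depends on sample size as well as on the gap, and not at all on how strongly the variable predicts outcome. Conversely, five independent tests at 0.05 would flag at least one chance difference in 1 − 0.95^5 = 22.6% of trials.

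**What an unadjusted split could do.** Assume that prior concussion doubles repeat-injury risk and that the App has no effect. With risk r in those without history, expected risk is r(1 + 17/64) in the App arm and r(1 + 27/64) in Usual Care. The expected risk ratio is (64 + 17)/(64 + 27) = 81/91 = 0.89. The mirror-image split would push the ratio the other way.

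**How often, and what happens overall.** Given 44 of 128 with history, a split at least as extreme as 17 vs 27 in that direction has hypergeometric probability 4.7%. The chance of a one-sided result favouring an ineffective App, under the same doubling and with no adjustment, was simulated:

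| Overall event rate | Given the 17 vs 27 split | Averaged over randomisation | Nominal |
|---|---|---|---|
| 16% | 4.3% | 2.4% | 2.5% |
| 37% | 6.9% | 2.7% | 2.5% |

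**Room for covariates in the repeat-injury model.** At 128 analysed under scenario 1, expected events are 64 × 0.16 + 64 × 0.02 = 11.5. The listed candidates number six if mental health and learning disabilities count separately. With treatment that makes seven terms, or 11.5 / 7 = 1.6 events per term.

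**The case against.** The strongest reply is that nothing here damages the trial's error rates. Randomisation already protects the unadjusted comparison, and the averaged rates of 2.4% and 2.7% bear that out. This stands. A reader might infer from the 4.3% and 6.9% figures that the plan inflates false positives in general. It does not: those rates hold only after a split that arises in about one randomisation in twenty, and the opposite split is equally likely.

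A reader might also infer that the tests miss over half of 15-point imbalances. For a true 15-point difference centred on 34%, the miss rate is 56% at 64 per arm but 48% at 80, the natural size for baseline data. It runs from about 40% to 60% across base rates of 17% to 50%. More fundamentally, these are errors about a population difference that randomisation rules out, so they do not measure how the plan would perform.

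Three further points limit the case:
- Concussion history is not only tested, since numbers of injuries are also described. Time since last injury is a listed confounder and might carry some of the same information, although the term is undefined and may mean the index injury.
- The twofold risk in section 2 concerns concussed children in general. Every participant is concussed, so it does not compare those with and without an earlier concussion.
- Section 9.5 sets no p-value rule and does not say that a variable judged similar will go unadjusted. That consequence is a reading of the text.

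None of this rescues the stated purpose of the tests, or explains why concussion history is missing from the list.

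**Conclusion.** The point holds as a correction to the analysis plan. Significance tests at 64 to 80 per arm cannot ensure that randomised groups are similar. Covariates should be chosen in advance on prognostic grounds, and concussion history has a better claim in the protocol's own background than its present treatment reflects. It bears on repeat injury as a presented risk factor and on symptom duration through the link with prolonged symptoms.

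The size is modest. The benefit is protection against an unlucky draw, illustrated by a shift in the expected risk ratio to about 0.89, plus some precision that was not quantified. The illustration rests on three assumptions: a doubling of risk, a 34% base rate taken from a follow-up clinic when recruitment also covers emergency departments, schools and community physicians, and a 0.05 level for the baseline tests. Overall type I error is not at issue.

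**What to change.** In section 9.5, replace the testing sentence with: *Baseline variables will be summarised by randomised arm without significance tests, and covariates are prespecified on prognostic grounds.*

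In the Cox model for time to symptom resolution, prespecify prior concussion (yes/no) as a covariate whatever the observed balance, and name any other covariates at the same time.

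In the repeat-injury model, do not simply add it to the present candidates. Replace that list with a short prespecified one, and include prior concussion only within it, because about 12 expected events will not support the current set.

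The cost is a few sentences in section 9.5 and no new data, since concussion history is already collected. The statistical price is one degree of freedom in the Cox model and fewer other covariates in the logistic model.

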9.6. DATA STORAGE AND SECURITY

Physical files are stored in the locked cabinets in CanChild (IAHS 408) with keys only held by 3 research staff. Computers for this project are located in CanChild. A username and password are required for access onto the computers/network and study specific documents are further restricted to the study team. Access to all data would require a data log to be completed. The Secure Network belongs to McMaster University and stored in a tier 4 data facility. The data centre is physically located in Hamilton, ON. Hamilton Health Sciences and McMaster University provides physical building security employing a card access system. There is a Cisco ASA Firewall in place. The server is running Windows 2008 R2 version. Any data from surveys will be completed online, deidentified, and stored onto REDCAP (https://canchild.mcmaster.ca/). REDCap (Research Electronic Data Capture) is a secure web application for building and managing online surveys and databases (www.project-redcap.org). As in several Canadian pediatric academic centers, REDCap has been set up in CanChild Centre for Childhood Disability Research at McMaster University to support research. Data is stored on a secure, firewall protected server with regular backup in the Faculty of Health Sciences Computer Services Unit with only the https port available to the internet. Data can be entered by designated users or survey respondents from any computer with an internet connection. Data will be anonymized upon entry and stored for 10 years. All data collected by The Back2Play App is stored locally on an anonymized relational database

All data collected by The Back2Play App is stored locally on an anonymized relational database through McMaster's Research and High Performance Computing Service. The data will be analyzed within this database and downloaded to study computers by the research staff all in deidentified form. All Personal Health Information will be stored within a REDCAP form which will be separate from all participant devices and the App database. For example, the participant would not use their name as an identifier but would be given a code assigned by the research staff.

Appendix 1.1 Business Rules for In-App Notifications

Progression through the CanChild RTA/RTS Guideline

- 1. Participants cannot enter RTA Stage 4 until they have completed RTS Stage 1-3
 - o If the participant reports RTA Stage 4 when they are in RTS Stage 1 or 2 they will receive the message "Stage 1, 2 and 3 come before RTA Stage 4!"
- 2. Participants must complete RTS Stage 5 (Full Return to School) before they can enter RTA Stage 4.
 - If the participant reports RTA Stage 4 or 5 when they are in RTS Stage 3 through 5, they will receive the message "You should complete RTS Stage 4-5 before RTA Stage 4-6".
- 3. Participants will be recommended to move to Stage 2 of RTS after 7 days
 - o If the participant reports RTS Stage 1 for 7 days, they will receive the message "You reported being in Stage 1 for 1 week, time to move to Stage 2!"
- 4. Participants will be recommended to move to Stage 3 of RTS after 14 days
 - o If the participant reports RTS Stage 2 for 14 days, they will receive the message "You reported being in Stage 2 for 2 weeks, time to move to Stage 3!"
- 5. Once in RTS Stage 3, participants cannot move back to Stage 2.
 - o If the participant reports RTS Stage 3 and moves back to RTS Stage 2, they will receive the message "Once your reach RTS Stage 3, you should not return to RTS Stage 2".

- 6. Participants are recommended to complete RTA and RTS Stage 1-3 together.
 - o If the participant reports RTA Stage 3 while in RTS Stage 1 or 2, they will receive the message "Remember, RTS and RTA Stage 1 to 3 should go together!"
- 7. Participants will be cautioned when they try and skip a stage
 - o If the participant skips from RTS Stage 2 to RTS Stage 4, they will receive the message "You forgot RTS Stage 3, we recommend you log this stage first!"
- 8. Participants will be cautioned when they try to move back a stage.
 - o If the participant moves back a Stage i.e., RTS Stage 5 to Stage 4, RTA 5 to Stage 4 they will receive the message "*Are you sure you want to move back a stage?*"
- 9. Participants cannot progress to a new stage of RTA/RTS if 2 or more symptoms worsen
 - o If the participant reports that 2 or more symptoms worsen (from morning to evening survey), **and** the participant attempts to progress to a new stage, they will receive the message "We recommend you do not progress to a new stage and inform a parent of your symptoms".
- 10. Participants cannot progress to a new stage of RTA/RTS if their total number of symptoms increases by 2.
 - o If the participant reports an increase in symptoms by 2 (from morning to evening survey) **and** the participant attempts to progress to a new stage, they will receive the message "We recommend you do not progress to a new stage and inform a parent of your symptom".

CanChild RTA/RTS Symptom Strata

- 11. Participants will be classified to Strata A (Symptom Free within 48 hours after Injury) if their initial symptoms disappear within 24 hours or after 24-48 hours a participant reports ≤ 2 symptoms.
 - o If symptoms worsen, a participant can transition to Strata B.
 - o If the participant reports that their symptoms disappear within 24 hours, they will receive the message "Take at least 24 hours for each Stage as you complete the guidelines".
- 12. Participants will be classified to Strata B (Symptom Free/Symptoms decreases within 1-4 weeks post injury) if the report > 2 initial symptoms at 50 hours and continue at > 2 for 1 week (168 hours) up to 4 weeks. If the child's symptoms decrease, but are still >2, the child should remain in stratum B.
 - o Once a participant is in Strata B, they can never go to Strata A.
 - o If a participant is in Strata B and progressing through Stages within 2 days, but symptoms are getting worse, the child should take longer to progress through the stages.
 - o If > 2 Symptoms for a month, move the participant to Strata C

- o Recommendation: "Take at least 48 hours for each Stage as you complete the guidelines".
- 13. Participants will be classified to Strata C (Symptomatic for more than 4 weeks) if they report ≥ 2 initial symptoms for ≥ 4 weeks, or if the participant has been in Strata B for 1 month.
 - Once a participant is in Strata C, they can never go to Strata A or B.
 - o Recommendation: "Take at least 1 week for each Stage as you complete the guidelines".

Increasing or Worsening Symptoms

- 14. Participants will be reminded to share their symptoms with their parents if their number of symptoms increases by 2
 - o If the participant reports 2 or more symptoms new symptoms, they will receive the message "We recommend you inform a parent of your symptoms".
- 15. Participants will be reminded to share their symptoms with their parents if 2 or more symptoms worsen.
 - o If the participant reports 2 or more symptoms worsen, hey will receive the message "We recommend you inform a parent of your symptoms".
- 16. Participants will be recommended to slow down if their number of symptoms increases by 2
 - o If the participant reports >=2 symptoms are reported worse at all 3 surveys (3x in one day), they will receive the message "Slow down! Take a rest".
- 17. Participants will be provided positive feedback if their number of symptoms increases by 2
 - o If the participant reported >=2 Symptoms logged Better, they will receive the message "Symptoms got better, Great job!"

Activity Recommendations

- 18. Participants will be recommended to reduce their activity if they exceed the following cut points:
 - RTA Stage 1: 5 mins of light activity
 - RTA Stage 2: 60 mins of light activity
 - RTA Stage 3: 120 mins of moderate activity
 - RTA Stage 4: up to 180 mins of vigorous activity
 - RTA Stage 5: Unlimited activity *No Contact
 - RTA Stage 6: Unlimited *Contact
 - o Light activity < 40 steps per minute (Stage 1-2)
 - o Moderate activity 40-93 steps per minute (Stage 3)
 - \circ MVPA \ge 94 steps per minute (Stage 4)
 - o Vigorous (Stage 5-6) doesn't need to be distinguished
 - If the participant exceeds activity recommendations for RTA Stage 1 to 4 and symptoms increase, they will receive the message "Slow down!"

- If the participant exceeds activity recommendations for RTA, they will receive the message "You did a lot of activity today!"
- If the participant meets activity recommendations for RTA Stage 1 to 4, they will receive the message "Great job today!"
- 19. Participants will be cautioned to reduce their activity if their heart rate exceeds 180 bpm
 - o If a child exceeds 180 bpm, the Back2Play App sends a cautionary they will receive the message "You are doing too much!"
 - o If the participant within Stage 1-3 and HR exceeds 180 bpm more than once within an hour, second notification is sent up to 3 notifications/day.

HR, bpm	Excepted	If exceeds, send Notifications
Resting	70-85	100
Peak	180	>180

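### As printed, the plan cannot fully measure time through all six RTA stages, and the App's stage-order triggers are narrower than rule 2's own message

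*Combined protocol and SAP*

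**What the plan says.** **Measurement.** Section 2 describes five RTS stages and six RTA stages. Section 8 makes time through all six RTA stages part of secondary outcome 2, and its Time to Stage paragraph derives time to each stage, and completion of the guidelines, from self-reported stage in both groups. Section 7 gives the daily self-rating as running to 5 or 6 in both groups, and ends the daily surveys two days after symptom resolution. The follow-up interview comes at that point, and App users delete the App during it. A REDCap survey on reinjury follows three months after enrolment. In Appendix 1.2 every legible RTA question offers 1 to 5. Appendix 1.6 asks whether the youth is fully back at school and sport, without asking when.

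**Stage-order messages (Appendix 1.1).** Rule 2 is headed "Participants must complete RTS Stage 5 (Full Return to School) before they can enter RTA Stage 4", and its message is "You should complete RTS Stage 4-5 before RTA Stage 4-6". The printed triggers are:

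- Rule 1: "If the participant reports RTA Stage 4 when they are in RTS Stage 1 or 2 they will receive the message".
- Rule 2: "If the participant reports RTA Stage 4 or 5 when they are in RTS Stage 3 through 5".
- Rule 6: RTA 3 reported at RTS 1 or 2.
- Rule 7: headed "Participants will be cautioned when they try and skip a stage", with the single trigger "If the participant skips from RTS Stage 2 to RTS Stage 4, they will receive the message".

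Rule 18 sets no minute limit at RTA 5 ("RTA Stage 5: Unlimited activity *No Contact") or at RTA 6.

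**The concern.** Time to the final RTA stage needs two things: a response option for that stage, and follow-up that lasts until it is reached. The printed App list lacks the first. The survey stop may cut off the second, because Section 2 bars contact sport and high-level activity while symptoms last, and RTA 6 is the contact stage. No later source of the date is planned, and Section 9.5 gives no censoring rule for this outcome.

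The messages are part of the intervention under test. A youth at RTS 1-2 is messaged for reporting RTA 3 or RTA 4, yet no printed trigger responds to a report of RTA 5, which is less restricted. As written, the triggers do not carry out the order that rule 2 states.

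**Working it through.** No sample size or power figure is at issue, so there is no stated figure to reproduce.

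**1. Response options.** Section 2, Section 7 and secondary outcome 2 all point to six RTA stages. The legible lists in Appendix 1.2 stop at 5, and there is no panel for a sixth stage. One panel's RTA question line is damaged in the text available, though its remaining option list also stops at 5. The Usual Care REDCap options are not printed.

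**2. Survey stop.** The App's minimum pacing (rules 11 to 13) is 24 hours, 48 hours or one week per stage for strata A, B and C; for stratum C the wording is "Take at least 1 week for each Stage as you complete the guidelines". Let k be the first RTA stage that must be symptom-free, and let d be days per stage. If k is entered on the day symptoms resolve, the earliest entry to RTA 6 is (6 − k) × d days later.

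| k (assumed) | A, d = 1 | B, d = 2 | C, d = 7 |
|---|---|---|---|
| 6 | 0 | 0 | 0 |
| 5 | 1 | 2 | 7 |
| 4 | 2 | 4 | 14 |

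The last survey is at day 2. Three of the nine values fall after it (7, 4 and 14 days) and six fall at or before it. The value of k is an assumption, because Section 2 does not say which RTA stage counts as high-level activity. The pacing is the App's; none is given for Usual Care.

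**3. Trigger grid.** Rules 1, 2 and 6 applied to each combination, giving the rule that sends a message:

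| | RTS 1 | RTS 2 | RTS 3 | RTS 4 | RTS 5 |
|---|---|---|---|---|---|
| RTA 3 | 6 | 6 | none | none | none |
| RTA 4 | 1 | 1 | 2 | 2 | 2 |
| RTA 5 | none | none | 2 | 2 | 2 |
| RTA 6 | none | none | none | none | none |

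Rule 2 clearly bars RTA 4 or above at RTS 1-4.

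- If the App offers RTA 1-5, there are 4 × 2 = 8 barred combinations and 2 are silent (RTA 5 at RTS 1 and at RTS 2).
- If it offers RTA 1-6, there are 4 × 3 = 12 and 6 are silent (those two, plus RTA 6 at RTS 1 to 4).

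RTA 6 at RTS 5 breaches the order only if RTS 5 is unfinished, so it is not counted.

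**4. Allowing for rule 7.** The grid leaves out skip messages, so upward moves are counted with RTS held fixed.

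- Into RTA 5 at RTS 1-2: 4 starting stages × 2 RTS stages = 8 moves. On rule 7's literal trigger all 8 are silent. If rule 7 covers every skip, 2 are silent (the step from RTA 4 at each RTS stage).
- Into RTA 6 at RTS 1-4, if offered: 5 starting stages × 4 RTS stages = 20 moves. On the literal trigger all 20 are silent. If rule 7 is general, 4 are silent (the step from RTA 5 at each RTS stage).

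RTA 4 draws a message at every RTS stage, so a youth who climbs one stage at a time has already been messaged there. At RTS 3-4, rule 2 messages again at RTA 5.

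**The case against.** The best defence is that rule 7's heading is general. Rule 8 has the same layout, a general heading followed by examples, so the bullets may illustrate rather than list every trigger. On that reading the silent moves shrink to single steps after an earlier message. Rules 3 and 4 also prompt youth to leave RTS 1 after 7 days and RTS 2 after 14 days, after which rule 2's trigger applies. This largely stands: a reader might take 6 of 12 as the size of the gap, but that count ignores skip messages. It does not remove the gap, since rule 7 prints no RTA trigger and its message names RTS Stage 3.

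The missing option 6 may be a slip in the appendix. Section 7 allows for a sixth stage, and Section 2 calls Appendix 1.2 a summary. That also stands. A reader might infer that the live App cannot record RTA 6, or that the missing option and the missing RTA 6 trigger both apply. The documents support neither. The two are alternatives: with options 1-5 the RTA 6 trigger is moot, and with options 1-6 the response-option problem disappears.

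A reader might also infer that RTA 6 usually falls after the last survey. That is not shown, since six of the nine values lie at or before day 2. The values are earliest times, however, and the plan has no means of dating a later entry.

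Finally, the messages only advise. The symptom rules (9 and 10) and the heart-rate rule (19) still apply at every RTA stage, and the App is an adjunct to medical care.

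**Conclusion.** The point holds as a minor one, in two separate parts.

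First, secondary outcome 2 is not fully measurable as printed. The App list stops at RTA 5 unless that is a print slip. Even with option 6 added, reports in both arms end two days after resolution, which is too early in three of the nine pacing scenarios (by 2, 5 or 12 days at the earliest: 4 − 2, 7 − 2, 14 − 2). This rests on the assumed symptom-free stage and on the App's minimum pacing. How often it would occur is unknown.

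Second, the stage-order triggers do not match rule 2's message. RTA 5 at RTS 1-2 has none, and neither does RTA 6 if it is offered. If rule 7 is general, only the single steps from RTA 4 to 5 at RTS 1-2 and from RTA 5 to 6 are silent.

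A reader might go on to infer that recovery or reinjury results would be distorted. The documents do not support that: the live App is not visible, the frequency of such moves is not given, and no effect on outcomes is claimed.

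**What to change.** - **Options:** offer RTA 1-6 in the App survey and Appendix 1.2, and confirm the same options in the Usual Care REDCap survey.
- **Date:** in the already planned 3-month survey, ask both arms for the date of reaching RTA 6. If it has not been reached, censor at the last contact. The drawback is a recalled date. The survey's timing should also be settled, since Section 7 counts three months from enrolment and Section 8 (Rate of Reinjury) from symptom resolution.
- **Rule 1:** extend the trigger to RTA 4-6 at RTS 1-2, and reword its message, which now names only RTA 4, to RTA Stage 4-6.
- **Rule 2:** extend the trigger to RTA 6 at RTS 3-4. Leave RTS 5 out, so that youth who have finished it get no new message.
- **Rule 7:** make the trigger and the message generic for any RTS or RTA skip.
- **Check:** compare the live App with the revised appendices.

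With rules 1 and 2 widened, all 12 barred combinations (RTS 1-4 with RTA 4-6) draw a message. The cost is a small change to notification logic, one response option, one date question and edits to two appendices. No visits are added.
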